4.3. Extent of Exposure

4.3.1. Duration of Exposure to Study Drugs

Duration of exposure to IDELA will be defined as minimum of (last IDELA dosing date, data cutoff date) – first IDELA dosing date +1, regardless of temporary interruptions in study drug administration, and will be expressed in months. For subjects who are randomized to Arm A, exposure duration will reference to the first dosing date of IDELA in Study GS-US-312-0116.

Duration of exposure to IDELA will be summarized for the FAS using descriptive statistics and as the number and percentage of subjects exposed for at least 2, 4, and 6 months, and every 6 months thereafter.

Number and percentage of subjects who had IDELA dose modification (dose reduction and dose re-escalation) will also be summarized. IDELA dosing records, drug accountability (dispense and return), and dose modification records will be listed in detail.

4.4. **Protocol Deviations**

Protocol deviations will be categorized before database finalization by Gilead. The important (major) protocol deviations will be summarized by type of deviation in the clinical study report (CSR) for subjects who enroll into Study GS-US-312-0117. A listing will be provided for important protocol deviations.

5. BASELINE DATA

5.1. Demographics and Baseline Characteristics

Demographics including gender, race, ethnicity, age (years), weight (kg), height (cm), and body mass index (BMI, kg/m²) will be summarized for the FAS. Gender, race, ethnicity, and Karnofsky performance status will be summarized by using summary statistics for categorical variables. Age (years), weight (kg), and height (cm) will be summarized using summary statistics for continuous variables. Age will be calculated as the number of years between date of birth and date of randomization in Study GS-US-312-0116.

Age (years) = (date of randomization in Study GS-US-312-0116 – date of birth + 1) / 365.25 (round down to an integer)

BMI $(kg/m^2) = weight / (height)^2$ (round to 1 decimal point)

Number and percentage of subjects < 65 and ≥ 65 years will also be summarized. A data listing will be presented.

5.2. Medical History

A listing of total cumulative illness rating scale (CIRS) scores and medical history will be provided.

6. EFFICACY ANALYSES

An IRC was established for this study and includes primary board-certified radiologists and a board-certified adjudicating radiologist from a pool of radiologists, and an independent board-certified hematologist or oncologist to perform an independent review of response and disease progression for each subject. The review will comprise an assessment of radiographic images and prospectively defined clinical data acquired during the study according to the Gilead Protocol GS-US-312-0117 Imaging Charter. The determination of CLL response and progression will be based on standardized criteria promulgated by the International Workshop on CLL (IWCLL) {12154}, as specifically modified for this study to reflect current recommendations which consider the mechanism of action of IDELA and similar drugs {22541}. The findings of the IRC will be considered primary for analyses of tumor control endpoints.

6.1. Efficacy Endpoints

6.1.1. Definition of Efficacy Endpoints

- Progression-free survival (PFS) defined as the interval from the baseline reference date for efficacy endpoints, as defined in Section 3.5.1, to the earlier of the first documentation of definitive disease progression or death from any cause; definitive disease progression is CLL progression based on standard criteria {12154}, {22541} other than lymphocytosis alone.
- Overall response rate (ORR) defined as the proportion of subjects who achieve a complete response (CR) or partial response (PR)
- Lymph node response (LNR) rate defined as the proportion of subjects who achieve a
 ≥ 50% decrease from baseline in the sum of the products of the greatest perpendicular
 diameters (SPD) of index lesions per IRC assessments
- Complete response (CR) rate defined as the proportion of subjects who achieve a CR
- Time to response (TTR) defined as the interval from the baseline reference date for efficacy endpoints to the first documentation of CR or PR
- Duration of response (DOR) defined as the interval from the first documentation of CR or PR to the earlier of the first documentation of definitive disease progression or death from any cause
- Percent change in lymph node area defined as the percent change from baseline in the SPD of index lymph nodes
- Splenomegaly response rate defined as the proportion of subjects with baseline splenomegaly who achieve an on-study normalization or a 50% decrease (minimum 2 cm) from baseline in the enlargement of the splenic longest vertical dimension (LVD) by imaging.

- Hepatomegaly response rate defined as the proportion of subjects with baseline hepatomegaly who achieve an on-study normalization or a 50% decrease (minimum 2 cm) from baseline the hepatic LVD by imaging.
- Absolute lymphocyte count (ALC) response rate defined as the proportion of subjects with baseline lymphocytosis (ALC $\ge 4 \times 10^9$ /L) who achieve an on-study ALC $< 4 \times 10^9$ /L or demonstrate a $\ge 50\%$ decrease in ALC from baseline; ALC values within 4 weeks post-baseline will be excluded from the ALC response rate evaluation.
- Platelet response rate defined as the proportion of subjects with baseline thrombocytopenia (platelet count $< 100 \times 10^9/L$) who achieve an on-study platelet count $\ge 100 \times 10^9/L$ or demonstrate a $\ge 50\%$ increase in platelet count from baseline without need for exogenous growth factors. Platelet values within 4 weeks post-baseline or after 8 days post transfusion will be excluded from the platelet response rate evaluation.
- Hemoglobin response rate defined as the proportion of subjects with baseline anemia (hemoglobin < 110 g/L [11.0 g/dL]) who achieve an on-study hemoglobin ≥110 g/L (11.0 g/dL) or demonstrate a ≥ 50% increase in hemoglobin from baseline without red blood cell transfusions or need for exogenous growth factors. Hemoglobin values within 4 weeks post-baseline or after 4 weeks of receiving packed cell/whole blood transfusion or after 6 weeks receiving exogenous growth factors (e.g., Darbepoetin alfa) will be excluded for the hemoglobin response evaluation.
- Neutrophil response rate defined as the proportion of subjects with baseline neutropenia (absolute neutrophil count [ANC] ≤ 1.5 × 10⁹/L) who achieve an ANC > 1.5 × 10⁹/L or demonstrate a ≥ 50% increase in ANC from baseline without need for exogenous growth factors. ANC values within 4 weeks of post-baseline or after 2 weeks of receiving exogenous growth factors (e.g., Filgrastim, G-CSF, Lenograstim) or after 4 weeks of receiving Neulasta will be excluded for the neutrophil response evaluation.
- Overall Survival (OS) defined as the interval from the date of randomization in Study GS-US-312-0116 to death from any cause during the study or long term follow up
- Change from baseline in HRQL using FACT-Leu scores
- Changes from baseline in Karnofsky performance status
- Change from baseline in overall health and summary of single-item dimension scores as assessed using the EuroQoL Five-Dimension (EQ-5D) utility measure

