Note: At the Investigator's discretion, subjects who were randomized to placebo on study GS-US-312-0116 may delay initiation of idelalisib following enrollment on Study GS-US-312-0117 until the time of disease progression or until the investigator determines that the subject would benefit from initiation of idelalisib treatment

Reference Therapy, Dose, and Mode of Administration:

Not applicable

Criteria for Evaluation:

Tumor Control

- Progression-free survival (PFS) defined as the interval from the start of study therapy to the earlier of the first documentation of definitive disease progression or death from any cause; definitive disease progression is CLL progression based on standard criteria other than lymphocytosis alone
- Overall response rate (ORR) defined as the proportion of subjects who achieve a complete response (CR) or partial response (PR)
- Lymph node response rate defined as the proportion of subjects who achieve a ≥50% decrease from baseline in the sum of the products of the greatest perpendicular diameters (SPD) of index lesions
- CR rate defined as the proportion of subjects who achieve a CR
- Time to response (TTR) defined as the interval from start of study therapy to the first documentation of CR or PR
- Duration of response (DOR) defined as the interval from the first documentation of CR or PR to the earlier of the first documentation of definitive disease progression or death from any cause
- Percent change in lymph node area defined as the percent change from baseline in the SPD of index lymph nodes
- Splenomegaly response rate defined as the proportion of subjects with baseline splenomegaly who achieve an on-study normalization or a 50% decrease (minimum 2 cm) from baseline in the enlargement of the splenic LVD (by imaging)

- Hepatomegaly response rate defined as the proportion of subjects with baseline hepatomegaly who achieve an on-study normalization or a 50% decrease (minimum 2 cm) from baseline the hepatic longest vertical dimension (LVD) (by imaging)
- ALC response rate defined as the proportion of subjects with baseline lymphocytosis (ALC≥4 x 10⁹/L) who achieve an on-study ALC <4 x 10⁹/L or demonstrate a ≥50% decrease in ALC from baseline (ALC values within 4 weeks post-baseline will be excluded from the ALC response rate evaluation)

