3.1. Endpoints

3.1.1. Tumor Control

- Progression-free survival (PFS) defined as the interval from the start of study therapy to the
 earlier of the first documentation of definitive disease progression or death from any cause;
 definitive disease progression is CLL progression based on standard criteria other than
 lymphocytosis alone
- ORR defined as the proportion of subjects who achieve a CR or partial response (PR)
- Lymph node response rate defined as the proportion of subjects who achieve a ≥50% decrease from baseline in the SPD of index lymph nodes
- CR rate defined as the proportion of subjects who achieve a CR
- Time to response (TTR) defined as the interval from start of study therapy to the first documentation of CR or PR
- Duration of response (DOR) defined as the interval from the first documentation of CR or PR to the earlier of the first documentation of definitive disease progression or death from any cause

- Percent change in lymph node area defined as the percent change from baseline in the sum of the products of the greatest perpendicular diameters (SPD) of index lymph nodes
- Splenomegaly response rate defined as the proportion of subjects with baseline splenomegaly who achieve an on-study normalization or a 50% decrease (minimum 2 cm) from baseline in the enlargement of the splenic LVD (by imaging)
- Hepatomegaly response rate defined as the proportion of subjects with baseline hepatomegaly who achieve an on-study normalization or a 50% decrease (minimum 2 cm) from baseline in the hepatic longest vertical dimension (LVD) (by imaging)
- ALC response rate defined as the proportion of subjects with baseline lymphocytosis (ALC≥4 x 10⁹/L) who achieve an on-study ALC <4 x 10⁹/L or demonstrate a ≥50% decrease in ALC from baseline; ALC values within 4 weeks post-baseline will be excluded from the ALC response rate evaluation
- Platelet response rate defined as the proportion of subjects with baseline thrombocytopenia (platelet count <100 x 10^9 /L) who achieve an on-study platelet count ≥ 100 x 10^9 /L or demonstrate a $\ge 50\%$ increase in platelet count from baseline; platelet values within 4 weeks post-baseline or after 8 days post transfusion will be excluded from the platelet response rate evaluation

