7.4.2. Spleen and Liver

Both the spleen and liver will be assessed by CT/MRI scan at baseline and at the stipulated intervals during treatment. The baseline and nadir values for the longest vertical dimension (LVD) of each organ will be used as reference to further characterize the objective tumor response of the measurable dimensions of the CLL during treatment. All spleen and liver LVD measurements should be recorded in centimeters.

By imaging, the spleen will be considered enlarged if it is >12 cm in LVD {Asghar 2011, Bezerra 2005}.

For subjects with splenomegaly at baseline or at the splenic LVD nadir, respective response and progression evaluations of the spleen will consider only changes relative to the enlargement of the spleen at baseline or nadir, not changes relative to the total splenic LVD.

A 50% decrease (minimum 2 cm) from baseline in the enlargement of the spleen in its LVD or decrease to \leq 12 cm in the LVD, is required for declaration of a splenomegaly response. Conversely, an increase in splenic enlargement by \geq 50% from nadir (with a minimum 2 cm increase) is required for declaration of splenic progression.

By imaging, the liver will be considered enlarged if it is >18 cm in LVD {Erturk 2006}.

A 50% decrease (minimum 2 cm) from baseline in the enlargement of the liver in its LVD or decrease to \leq 18 cm in the LVD is required for declaration of a hepatomegaly response. Conversely, an increase in liver enlargement by \geq 50% from nadir (with a minimum 2 cm increase) is required for declaration of hepatic progression.

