7.5.2. Partial Response

To satisfy criteria for a PR, all of the following criteria must be met:

- No evidence of new disease
- A change in disease status meeting ≥2 of the following criteria, with 2 exceptions in which only 1 criterion is needed: (1) Only lymphadenopathy is present at baseline;
 (2) Only lymphadenopathy and lymphocytosis are present at baseline. In these 2 cases, only lymphadenopathy must improve to the extent specified below:

- In a subject with baseline lymphocytosis (ALC $\ge 4 \times 10^9$ /L), a decrease in peripheral blood ALC by $\ge 50\%$ from baseline or a decrease to $\le 4 \times 10^9$ /L
- A decrease by $\geq 50\%$ from the baseline in the SPD of the index nodal lesions
- In a subject with enlargement of the spleen at baseline, a splenomegaly response, defined as a ≥50% decrease (minimum 2 cm) from baseline in the enlargement of the spleen or decrease to ≤12 cm in the LVD by imaging
- In a subject with enlargement of the liver at baseline, a hepatomegaly response, defined as a ≥50% decrease (minimum 2 cm) from baseline in the enlargement of the liver or decrease to ≤18 cm in the LVD by imaging
- A decrease by ≥50% from baseline in the CLL marrow infiltrate or in B-lymphoid nodules
- No index, splenic, liver, or non-index disease with worsening that meets the criteria for definitive PD
- Peripheral blood counts meeting ≥1 of the following criteria:
 - ANC >1.5 x 10^9 /L or >50% increase over baseline without need for exogenous growth factors (eg, G-CSF)
 - Platelet count ≥100 x 10⁹/L or ≥50% increase over baseline without need for exogenous growth factors or transfusions
 - Hemoglobin ≥ 110 g/L (11.0 g/dL) or $\ge 50\%$ increase over baseline without red blood cell transfusions or need for exogenous growth factors (eg, erythropoietin)

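### The hepatomegaly response endpoint halves the whole liver dimension, while the protocol's response criteria halve only the enlargement above 18 cm; the two need reconciling before Table 2.9 is programmed

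*SAP*

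**What the plan says.** The documents state the hepatomegaly response rule five times, in two forms.

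**Whole-dimension form (endpoint definitions)**
- SAP 6.1.1 counts subjects with baseline hepatomegaly who normalise or show a 50% decrease (minimum 2 cm) "from baseline the hepatic LVD by imaging".
- The protocol synopsis, under Criteria for Evaluation, reads "from baseline the hepatic longest vertical dimension (LVD) (by imaging".
- Protocol 3.1.1 reads "from baseline in the hepatic longest vertical dimension (LVD) (by imaging".

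**Enlargement form (response criteria)**
- Protocol 7.4.2, stating what is needed to declare a hepatomegaly response, takes the 50% decrease (minimum 2 cm) "from baseline in the enlargement of the liver in its LVD", or accepts a fall to 18 cm or less.
- Protocol 7.5.2, the hepatomegaly component of PR, has "from baseline in the enlargement of the liver or decrease to" 18 cm or less.

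The reference limit is in protocol 7.4.2: "By imaging, the liver will be considered enlarged if it is >18 cm in LVD".

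The spleen bullet directly above the liver bullet in SAP 6.1.1 uses the enlargement form: "from baseline in the enlargement of the splenic longest vertical dimension (LVD) by imaging". The synopsis and protocol 3.1.1 show the same difference between the two organs.

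Under SAP 6.1.2.7 the rate is calculated among subjects with the baseline abnormality and sufficient assessments, and is given with a 95% CI. SAP Appendix 1 lists it as Table 2.9, by IRC assessment.

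**The concern.** One named endpoint has two rules that classify the same subject differently. A programmer working from SAP 6.1.1 alone would apply a rule that, for most plausible liver sizes, recognises only normalisation. The SAP bullet neither cites protocol 7.4.2 nor restates its rule.

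Three things are at stake:
- The rate in Table 2.9 could come out lower than the protocol's own response criteria would give.
- A subject could meet the hepatomegaly criterion that counts towards PR under 7.5.2 and still be a non-responder in Table 2.9.
- The liver rate would not be on the same footing as the spleen rate in Table 2.8. Protocol 9.4.4.1 also names the hepatomegaly rate among the variables that may be compared across the two studies for Arm B.

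**Working it through.** The plan gives no figure to reproduce, so the check compares the two rules.

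**Inputs.** B is the baseline hepatic LVD in cm. Hepatomegaly means B > 18 (protocol 7.4.2). Normalisation means LVD of 18 or less. The 50% and the 2 cm minimum are in all five statements. Enlargement is taken as B − 18. The documents do not print that formula, but it follows from the 18 cm limit and from 7.4.2's separation of splenic enlargement from total splenic LVD.

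**Highest on-study LVD that still counts as a response**
- Literal rule: the larger of 18 and B − max(2, B/2). Since B/2 > 9, this is max(18, B/2).
- Protocol 7.4.2 rule: the larger of 18 and B − max(2, (B − 18)/2).

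**When the literal 50% branch adds anyone.** It needs B/2 > 18, so B > 18/0.5 = 36 cm. At or below 36 cm, a subject who halves the LVD has already normalised. The branch can be met there, but it is redundant.

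**When the 7.4.2 branch adds anyone.** While the 2 cm minimum governs, B − 2 > 18 requires B > 20 cm. The minimum governs while (B − 18)/2 < 2, that is B < 22 cm. Above that, the threshold is B/2 + 9, which exceeds 18 for every B > 18.

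**The 2 cm minimum under the literal rule.** Half of more than 18 cm is more than 9 cm, so the minimum can never bind.

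| Baseline LVD (cm) | Literal 50% target | Literal response threshold | 7.4.2 response threshold |
|---|---|---|---|
| 20 | 10 | 18 | 18 |
| 21 | 10.5 | 18 | 19 |
| 22 | 11 | 18 | 20 |
| 24 | 12 | 18 | 21 |
| 26 | 13 | 18 | 22 |
| 30 | 15 | 18 | 24 |
| 36 | 18 | 18 | 27 |
| 40 | 20 | 20 | 29 |

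**Direction.** For every B > 18 the literal threshold is at or below the 7.4.2 threshold. The literal rule is never the more lenient one, so any discrepancy lowers the rate.

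**Example.** A liver going from 24 to 21 cm has lost 3 cm of a 6 cm enlargement. That meets the hepatomegaly criterion in 7.5.2. Under SAP 6.1.1 as written it is neither normalised nor halved, so the subject is a non-responder.

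**Reach.** PR uses the enlargement form (7.5.2), CR requires normal liver size (7.5.1), and definitive progression uses hepatic enlargement (7.5.4). ORR, CR rate, PFS, TTR and DOR are built on those categories and do not use the endpoint bullet.

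**The case against.** The strongest reply is that the rule will be applied correctly despite the wording. Protocol 9.3.2.4 bases the individual response endpoints, liver size included, on the modified IWCLL criteria, and protocol section 7 sets those out. SAP section 6 makes IRC findings primary and refers to an imaging charter, and Table 2.9 is labelled as IRC assessment. The text also looks like an omission: the SAP and synopsis phrases are ungrammatical, the spleen bullet beside them is complete, and a 2 cm minimum that can never bind has no purpose.

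Much of this stands. It makes enlargement the likely intent, and it means literal programming cannot be assumed. It does not settle the derivation. The charter is not among the documents, and whether the IRC supplies an organ response or only measurements is not stated. Protocol 3.1.1 is grammatical and still refers to the whole dimension. Protocol 3.2.1 speaks loosely of reductions of at least 50% in spleen or liver size, but it covers both organs and the spleen endpoint is explicitly on enlargement, so it does not support a whole-liver rule.

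Three stronger readings might be inferred, and the documents do not support them:
- *The Table 2.9 rate is biased downward.* That holds only if the rule is programmed literally, which no document shows.
- *Every subject above 20 cm who halves the enlargement without normalising at that point is lost.* A subject who later normalises is counted, and above 36 cm the literal branch keeps some: at a baseline of 40 cm, a fall to 20 cm or less counts.
- *The SAP departed from the protocol's endpoint.* The SAP repeats the protocol's own endpoint definition; the conflict lies inside the protocol and is carried into the SAP.

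**Conclusion.** The inconsistency is real and should be corrected. As written, the endpoint rule reduces to liver normalisation for every baseline LVD up to 36 cm, whereas protocol 7.4.2 and 7.5.2 recognise further responders at every baseline above 20 cm. If Table 2.9 is programmed literally, its rate would be understated relative to 7.4.2. Up to 36 cm, the subjects missed are those who meet the enlargement criterion, including the 2 cm minimum, without ever normalising. Above 36 cm, they are those who meet that criterion without halving the whole LVD.

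The size cannot be stated. The documents give neither the number of subjects with baseline hepatomegaly nor the distribution of liver size, and the baselines tabulated are illustrations. The arithmetic rests on reading enlargement as the excess over 18 cm.

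The effect is confined to one component rate in an analysis that SAP 3.5.2 describes as descriptive, with no formal comparisons between treatment groups. A reader might suppose that the overall response results are compromised as well. They are not, because the PR, CR and progression definitions do not share the whole-dimension wording. Liver assessments are listed by subject (Listing 2.1.3), so the enlargement-based rate should be recoverable.

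**What to change.** Reword the liver endpoint in SAP 6.1.1, protocol 3.1.1 and the synopsis to match protocol 7.4.2 and 7.5.2. A response should be a fall to 18 cm or less, or a reduction of at least half, and at least 2 cm, in the amount by which the baseline hepatic LVD exceeds 18 cm. A cross-reference from SAP 6.1.1 to protocol 7.4.2 would prevent the two from drifting apart again. Then confirm that the Table 2.9 derivation follows this rule, whether the IRC delivers the organ response itself or only the measurements.

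The cost is the same one-sentence change in three places and a check or edit of one derivation. No new data are needed.

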- Platelet response rate defined as the proportion of subjects with baseline thrombocytopenia (platelet count <100 x 10⁹/L) who achieve an on-study platelet count ≥100 x 10⁹/L or demonstrate a ≥50% increase in platelet count from baseline without need for exogenous growth factors (Platelet values within 4 weeks post-baseline or within 8 days post transfusion will be excluded from the platelet response rate evaluation)
- Hemoglobin response rate defined as the proportion of subjects with baseline anemia (hemoglobin <110 g/L [11.0 g/dL]) who achieve an on-study hemoglobin ≥110 g/L (11.0 g/dL) or demonstrate a ≥50% increase in hemoglobin from baseline without red blood cell transfusions or need for exogenous growth factors (eg erythropoietin)
- Neutrophil response rate defined as the proportion of subjects with baseline neutropenia (absolute neutrophil count [ANC] ≤1.5 x 10⁹/L) who achieve an ANC >1.5 x 10⁹/L or demonstrate a ≥50% increase in ANC from baseline without need for exogenous growth factors (eg, G-CSF)

Patient Well-Being

- Overall survival (OS) defined as the interval from start of study therapy to death from any cause
- Change from baseline in HRQL domain and symptom scores based on the Functional Assessment of Cancer Therapy: Leukemia (FACT-Leu) (See Appendix 2)
- Changes from baseline in Karnofsky performance status (See Appendix 3)

Pharmacodynamic Markers of Drug Activity and Resistance

- Changes from baseline in PI3K/AKT/mTOR pathway activation as a measure of PI3Kδ pathway activity
- Changes from baseline in the plasma concentrations of disease-associated chemokines and cytokines

Exposure

- Study drug administration as assessed by prescribing records and compliance as assessed by quantification of used and unused drug
- Trough (pre-dose) and peak (~1.5-hour samples) of idelalisib plasma concentrations as assessed by a validated bioanalytical method

Safety

 Overall safety profile of each regimen characterized by the type, frequency, severity, timing of onset, duration, and relationship to study therapy of any adverse events or abnormalities of laboratory tests; serious adverse events; or adverse events leading to discontinuation of study drug

Pharmacoeconomics

- Change in health status defined as the change from baseline in overall health and single-item dimension scores as assessed using the EuroQoL Five-Dimension (EQ-5D) utility measure

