- Hemoglobin response rate defined as the proportion of subjects with baseline anemia (hemoglobin <110 g/L [11.0 g/dL]) who achieve an on-study hemoglobin ≥110 g/L (11.0 g/dL) or demonstrate a ≥50% increase in hemoglobin from baseline; hemoglobin values within 4 weeks post-baseline or after 4 weeks of receiving packed cell/whole blood transfusion or after 6 weeks of receiving exogenous growth factors (e.g., Darbepoetin alfa) will be excluded for the hemoglobin response evaluation

- Neutrophil response rate defined as the proportion of subjects with baseline neutropenia (absolute neutrophil count [ANC] ≤1.5 x 10⁹/L) who achieve an ANC >1.5 x 10⁹/L or demonstrate a ≥50% increase in ANC from baseline; ANC values within 4 weeks of post-baseline or after 2 weeks of receiving exogenous growth factors (e.g., Filgrastim, G-CSF, Lenograstim) or after 4 weeks of receiving Neulasta were excluded for response evaluation

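### Platelet response: SAP 6.1.1 and protocol 3.1.1 exclude counts taken after 8 days post transfusion, the synopsis those within 8 days; read literally, the SAP can keep transfusion-supported counts and drops the later ones

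*SAP*

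**What the plan says.** The platelet exclusion rule appears three times.

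- Protocol synopsis, Criteria for Evaluation: "Platelet values within 4 weeks post-baseline or within 8 days post transfusion will be excluded from the platelet response rate evaluation".
- Protocol 3.1.1: "increase in platelet count from baseline; platelet values within 4 weeks post-baseline or after 8 days post transfusion" are the values excluded.
- SAP 6.1.1: "Platelet values within 4 weeks post-baseline or after 8 days post transfusion will be excluded from the platelet response rate evaluation".

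The SAP definition adds a support clause, requiring an "increase in platelet count from baseline without need for exogenous growth factors". It does not mention transfusion. Protocol 3.1.1 has no support clause for platelets.

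For hemoglobin, the synopsis gives a support clause, "increase in hemoglobin from baseline without red blood cell transfusions or need for exogenous growth factors (eg erythropoietin", and no time window. Protocol 3.1.1 gives a window in the *after* form: "increase in hemoglobin from baseline; hemoglobin values within 4 weeks post-baseline or after 4 weeks of receiving packed cell/whole blood transfusion". For neutrophils it does the same: "increase in ANC from baseline; ANC values within 4 weeks of post-baseline or after 2 weeks of receiving exogenous growth factors". SAP 6.1.1 repeats those windows and restores support clauses, for hemoglobin "increase in hemoglobin from baseline without red blood cell transfusions or need for exogenous growth factors".

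SAP 6.2, which lists changes from the protocol's efficacy analyses, does not mention any of this.

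**The concern.** An exclusion window after a transfusion exists to stop donated platelets from being read as marrow recovery. The synopsis rule does that. The wording in protocol 3.1.1 and SAP 6.1.1 removes the opposite part of the post-transfusion record: it keeps the counts nearest the transfusion and discards all later ones, with no end date.

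For platelets the window is the only part of the SAP definition that deals with transfusion, so nothing else catches the supported counts once it is reversed. A program written from SAP 6.1.1 could produce a Table 2.11 that misses real unsupported recovery and credits transfusion effects to idelalisib.

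**Working it through.** **Which direction is intended.** Protocol 7.5.1 and 7.5.2 set the platelet criteria for CR and PR, and both require the count to be reached without transfusion as well as without growth factors. That agrees with the synopsis and not with *after 8 days*. The *after* form also has no upper limit, so one transfusion would disqualify every platelet count more than 8 days later.

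**Effect on scheduled counts.** The plan states no figure to reproduce, so this is an illustration. Inputs:

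- Hematology days in protocol Appendix 7 up to Day 337. Those more than 28 days after Day 1 are 43, 57, 71, 85, 113, 141, 169, 211, 253, 295 and 337, which is 11 values.
- One transfusion, on Day T; scheduled samples only; baseline at the first idelalisib dose.
- *After* rule: a count on Day d is dropped if d − T > 8. *Within* rule: dropped if 0 < d − T ≤ 8.

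| T | Kept under *after* | Dropped under *after* | Dropped under *within* |
|---|---|---|---|
| 30 | none | 11 | 0 |
| 50 | 43, 57 | 9 | 1 (Day 57) |
| 60 | 43, 57 | 9 | 0 |
| 80 | 43 to 85 | 7 | 1 (Day 85) |
| 140 | 43 to 141 | 5 | 1 (Day 141) |
| 300 | 43 to 295 | 1 | 0 |

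For T = 50: 57 − 50 = 7, so Day 57 is kept under *after* and dropped under *within*; 71 − 50 = 21, so Day 71 onward is dropped under *after* and kept under *within*.

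Two early cases follow. If T is any of Days 1 to 34, then T + 8 ≤ 42 and no scheduled value survives the *after* rule. If T is any of Days 35 to 42, only Day 43 survives, and it lies 1 to 8 days after the transfusion.

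Open-label subjects move to 12-weekly visits after 24 weeks of idelalisib (protocol 6.2). Days 211 and 295 then fall out, leaving 9 values; at T = 60 the *after* rule drops 7 and the *within* rule none.

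**Opportunity for a false response.** A scheduled count follows 1 to 8 days later for 11 × 8 = 88 of the 336 possible transfusion days (26%), or 9 × 8 = 72 of 336 (21%) on the open-label schedule. Unscheduled counts would alter these shares.

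**Effect of one misclassified subject.** With n evaluable subjects (not given; 20 and 40 assumed), one false response adds 1/n: 5.0 or 2.5 percentage points. A true responder counted as a non-responder subtracts the same. If that subject instead leaves the denominator, the rate p falls by (1 − p)/(n − 1). For n = 20 that is 0.5/19 = 2.6 points at an assumed p of 50%, with a range from 0.8/19 = 4.2 (p = 20%) to 0.2/19 = 1.1 (p = 80%).

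**The case against.** **Dropped counts are not lost responses.** This stands. One qualifying on-study value is enough, and values from before the transfusion (beyond 4 weeks post-baseline) are kept under both rules. A reader might infer from 9 dropped counts out of 11 that most transfused responders are lost; the documents do not support that. The loss also shrinks with later transfusions, to a single count at Day 300, and unscheduled or local counts may add values.

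**Hemoglobin and neutrophils.** A reader might infer that these windows are wrong in the same documented way. They are not: the synopsis gives no window for either, and protocol 3.1.1 and SAP 6.1.1 agree with each other. Their wording could even mean after a period of continuing support. The SAP's support clauses may also keep supported values from counting. What remains is an inference from the shared wording, the rule's purpose and the CR and PR criteria.

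**Two texts against one, and an obvious slip.** The protocol body and SAP agree, but agreement does not give the literal rule a purpose. A programmer may well guess what is meant; the SAP should still not need guessing.

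**Descriptive only, and traceable.** Also true. SAP 3.5.2 plans no formal comparisons, SAP 6.1.2.7 flags supportive care in listings, and a transfusion log is listed. Flags do not change the computed rate or its confidence interval.

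**Conclusion.** The platelet window in SAP 6.1.1 and protocol 3.1.1 is wrong as written and contradicts the synopsis. It should be corrected before Table 2.11 is programmed.

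A subject is misclassified only in two situations: there is no earlier qualifying value and genuine unsupported recovery comes later, or the only qualifying value is itself transfusion-supported. Only subjects with baseline thrombocytopenia who were transfused can be affected. Their number is not in the documents and could be zero, so the visit counts show the direction of the error and not its effect on the rate. They rest on one transfusion and nominal visits. Subjects randomized to Arm A are not illustrated, because the laboratory schedule of Study GS-US-312-0116 is not in these documents.

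The consequence is confined to a descriptive component rate; PFS, ORR, CR, DOR and OS do not use the window. For hemoglobin and neutrophils the conclusion is only that intent needs confirming.

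A separate matter is that SAP 6.1.2.7 limits these rates to subjects with sufficient assessments, whereas protocol 9.4.2.2 keeps insufficiently assessed subjects in the denominator, and SAP 6.2 does not list the difference. A reader might conclude that the protocol plainly retains a subject whose platelet counts are all excluded by rule. Its wording concerns tumor assessment, so that is not clear. The apparent difference would remain with the window corrected and adds no weight to the platelet point.

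**What to change.** 1. In SAP 6.1.1 and protocol 3.1.1, change the platelet exclusion from *after* 8 days to *within* 8 days post transfusion, matching the synopsis and the intent of protocol 7.5.1 and 7.5.2.
2. Before programming Tables 2.12 and 2.13, confirm the intended direction of the hemoglobin and neutrophil windows in the same two sections. If it is the same slip, change *after* to *within* and keep the stated durations: 4 weeks after red-cell or whole-blood transfusion, 6 weeks after erythropoietic factor, 2 weeks after G-CSF and 4 weeks after Neulasta.
3. Separately, reconcile the denominator rule in SAP 6.1.2.7 with protocol 9.4.2.2, and record it in SAP 6.2 if the SAP rule is intended.

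The cost is a few words in each document and a check of the derivation program. No new data are needed, since supportive-care flags and the transfusion log are already planned.
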